In our recent study, the early integrated PC intervention group had a median of seven PC visits per patient by week 24. Examining rates of cancer progression and hospitalizations from this study, we estimate that stepped care patients on step 1 of the intervention will have a median of three PC visits per patient by week 24, representing an approximate 60% reduction in PC resource utilization. If a patient is unable to be scheduled in person or via secure video visit within four weeks of the change in treatment or hospitalization, the PC clinician will attempt to contact them by telephone within the four weeks, document the call in the EHR, and the visit will be scheduled as soon as possible. If patients miss any scheduled PC visits during step 1, and the visit cannot be rescheduled within four weeks of the change in treatment or hospitalization, the PC clinician will attempt to contact the patient by telephone within seven days from the missed visit, document the call in the EHR, and the visit will be rescheduled as soon as possible. If the patient is unable to be reached by phone, the PC clinician will document the attempted contact or voicemail in the EHR. If the PC clinician does not speak Spanish, visits for Spanish-speaking patients will be conducted with the assistance of an interpreter or family member. During step 1, PC clinicians will attempt to communicate with oncology regarding what occurred in each visit, either by phone, email, personalized electronic communication, or in person.

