7.3. Exploratory Endpoints

- 7.3.1. To compare the longitudinal patterns in QOL in patients assigned to stepped PC versus early integrated PC, as measured by repeated assessments of FACT-L.
- 7.3.2. To compare the superiority of stepped PC versus early integrated PC with respect to cost-effectiveness.
- 7.3.3. To compare coping strategies in patients assigned to stepped PC versus early integrated PC.
- 7.3.4. To compare prognostic understanding in patients assigned to stepped PC versus early integrated PC.
- 7.3.5. To compare depression in patients assigned to stepped PC versus early integrated PC.
- 7.3.6. To compare health care utilization at the end of life (i.e., emergency department visits, hospitalizations, and chemotherapy administration) in patients assigned to stepped PC versus early integrated PC.

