We will assess the incremental cost-effectiveness of the early integrated PC arm relative to the stepped PC arm from the societal perspective using the average costs and quality adjusted life years (QALYs) accrued under each study arm and as follows: $(\text{Cost}_{\text{early integrated PC}} - \text{Cost}_{\text{stepped PC}}) / (\text{QALY}_{\text{early integrated PC}} - \text{QALY}_{\text{stepped PC}})$.⁶⁵ A \$50,000 per quality-adjusted life-year gained will be considered cost effective.⁶⁶ Costs will include all direct health care costs and indirect (time) costs incurred by patients over their life spans while enrolled in the trial.⁶⁷ The EQ-5D will be used to apply utility weights (quality adjustment) to patients' life spans. Both costs and QALYs will be discounted at a rate of 3%. Based on our prior trials, we expect that few patients will survive past the end of the study period.⁹ Cost and QALY data beyond the end of follow-up for those who are alive will be treated as missing data and estimated using multiple imputation methods. If we find that stepped care is non-inferior to early integrated PC in terms of both QALYs accrued and FACT-L scores, we will ignore QALY data and perform only a cost comparison between the study arms. We will use Monte Carlo methods using 10,000 simulations to incorporate uncertainty in parameter estimates and develop confidence bounds on the estimated cost-effectiveness ratio or the cost difference. Following standard methods of economic evaluation as we have done in other studies, we will also perform parameter-specific sensitivity analyses in which individual parameters are varied singly and in combination, through plausible ranges to assess the relative impact different elements of the program have on overall cost-effectiveness.^{68,69}

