## 7. Sample Size

Sample size calculations were performed to detect a non-inferiority margin of 4.5 points on the FACT-L at week 24, assuming a standard deviation of 17.5 points and a between-group difference of 0 points. 188 patients per group were required to achieve 80% power with a one-sided significance level of 0.05. To account for an anticipated 36% rate of missing data at week 24 due to loss-to-follow-up, withdrawal, or death, enrollment of 255 per group (510 total) was planned.

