## **9. Statistical Analysis**

### *Primary Outcome*

The primary outcome is patient-reported quality of life at week 24, as measured by the FACT-L. The difference in week 24 means between intervention groups will be estimated using a linear regression model with group assignment (stepped PC vs early integrated PC) and baseline FACT-L score, as well as randomization stratification factors, as main effects. Using the pre-specified non-inferiority margin of 4.5 points, non-inferiority of stepped PC will be established if the lower limit of the 90% confidence interval (CI) for the estimated difference in means is greater than -4.5. The corresponding p-value for non-inferiority will be calculated using a one-sided test of the estimated difference in means against a null value of -4.5 with a significance level of 0.05. Model-based estimates of the mean with 95% CI in each group, the difference in means between groups and its 90% CI, and the p-value will be reported.

To accompany the approach described above, we will also use a linear mixed effects regression model to estimate the difference in week 24 means between intervention groups. This model will utilize FACT-L scores at baseline, week 12, and week 24, with estimation via maximum likelihood. The model will include fixed effects for group assignment (stepped PC vs early integrated PC), time from baseline (in weeks), time-by-group interaction, and randomization stratification factors, as well as random intercepts for each patient. A contrast will be used to estimate the difference in means at week 24, and this estimate will be evaluated for non-inferiority in the same manner described above. This will be reported as a sensitivity analysis for evaluating non-inferiority for the primary outcome.

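### The cost-effectiveness plan drops QALYs once stepped PC is non-inferior, although non-inferiority does not show a zero QALY difference and no QALY margin is stated

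*Protocol*

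**What the plan says.** Protocol Section 7.3 lists the economic objective among the exploratory endpoints: "To compare the superiority of stepped PC versus early integrated PC with respect to cost-effectiveness". Section 7.5 plans the analysis as a ratio of the cost difference to the QALY difference between arms, with this threshold in dollars: "50,000 per quality-adjusted life-year gained will be considered cost effective".

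Section 7.5 then adds a conditional rule. The condition is "If we find that stepped care is non-inferior to early integrated PC in terms of both QALYs accrued and FACT-L scores", and the consequence is "we will ignore QALY data and perform only a cost comparison between the study arms". The Monte Carlo step follows the same branching, since it is meant to "develop confidence bounds on the estimated cost-effectiveness ratio or the cost difference". Once the rule applies, the planned bounds are therefore on cost alone. Section 7.5 also plans sensitivity analyses that vary individual parameters, but nothing says that QALYs return after the switch.

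The SAP does not replace this rule. Its Outcome Measures section states that the cost-effectiveness analysis is not described there. The documents give non-inferiority margins for FACT-L (4.5 points), EOL communication (10%) and hospice stay (7 days), but none for QALYs.

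**The concern.** A one-sided non-inferiority result says that a loss larger than the margin has been ruled out at the stated error level. It does not say that the loss is nil. A cost-only comparison is justified when the effects can be taken as equal; here it would follow a test that does not establish equality. The rule in effect sets the QALY difference to zero and removes its uncertainty from the reported interval.

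Three things follow.

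- **Sign of the conclusion.** A QALY loss small enough to pass can be worth more, at the protocol's own threshold, than the money saved. In the other direction, a QALY gain with stepped PC would be discarded.
- **Survival.** Costs are counted over the time patients live while enrolled, and EQ-5D weights are applied to that same time. Shorter survival lowers both costs and QALYs. A cost-only comparison would record it purely as a saving.
- **Trigger.** Without a QALY margin, nobody can say in advance which results activate the rule, and the margin could be set after the data are seen.

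The switch applies on the result the trial is designed to show, so it is not a remote branch of the plan.

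**Working it through.** **1. The plan's own figure.** FACT-L is the only gate with a stated margin. I take it to be the week-24 primary test. Inputs: margin 4.5, one-sided alpha 0.05 and 80% power, "assuming a standard deviation of 17.5 points and a between-group difference of 0 points" (SAP Section 7).

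n per group = 2 × [17.5 × (1.645 + 0.842) / 4.5]² ≈ 187.0 (187.003 with unrounded normal quantiles), rounded up to 188. This matches the stated 188; power at 188 is 80.2%.

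**2. What that gate lets through.** The SAP's criterion is that "non-inferiority of stepped PC will be established if the lower limit of the 90% confidence interval (CI) for the estimated difference in means" lies above −4.5.

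- With 188 per group, SE = 17.5 × √(2/188) = 1.805. The observed difference must exceed −4.5 + 1.645 × 1.805 = −1.53, so an observed deficit of up to 1.53 points passes.
- If the true deficit is 1 point, the chance of passing is Φ((4.5 − 1)/1.805 − 1.645) = Φ(0.294) = 0.62.
- With about 163 per group (255 × 0.64, the SAP's 36% missing), SE = 1.938, the largest passing deficit is 1.31 points, and the chance at a true 1-point deficit is 0.56.

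Passing the gate is thus compatible with a real deficit. The same holds in principle for a QALY gate.

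**3. Break-even QALY loss.** The net monetary benefit of stepped PC is (total cost saving) − 50,000 × (QALY loss). It turns negative when the loss exceeds saving / 50,000. The savings below are assumptions; the documents give no costs.

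| Assumed total saving per patient | Break-even QALY loss | Quality-adjusted days (× 365.25) |
|---|---|---|
| $600 | 0.012 | 4.4 |
| $800 | 0.016 | 5.8 |
| $1,200 | 0.024 | 8.8 |
| $2,400 | 0.048 | 17.5 |

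**4. The two analyses can disagree in sign.** Assume a saving of $800 and a true loss of 0.03 QALY.

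- Cost only: $800 in favour of stepped PC.
- Net benefit: 800 − 50,000 × 0.03 = 800 − 1,500 = −$700.

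The mirror case, $800 extra cost and a 0.03 QALY gain, gives −$800 on cost alone and 1,500 − 800 = +$700 in net benefit.

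**5. What an unstated margin could hide.** At $50,000 per QALY, a loss equal to a margin of 0.02, 0.05 or 0.10 QALY is worth $1,000, $2,500 or $5,000. The choice of margin therefore decides whether the losses that matter are screened out.

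**6. Why no frequency is given.** Take the QALY gate alone, with 255 per group, a true loss of 0.03, SE = SD × √(2/255), and chance of passing = Φ((margin − 0.03)/SE − 1.645).

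| Assumed margin | SD 0.2 | SD 0.3 | SD 0.4 |
|---|---|---|---|
| 0.10 | 0.99 | 0.84 | 0.63 |
| 0.05 | 0.30 | 0.19 | 0.14 |

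The answer runs from 0.14 to 0.99 depending on two quantities that the documents do not supply. Requiring FACT-L non-inferiority as well can only lower it.

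**The case against.** The strongest reply is about weight. Cost-effectiveness is exploratory, and Section 7.4 says that exploratory results will emphasise estimates and intervals. QALYs have to be estimated to test the gate at all, and FACT-L is reported with its interval. If stepped PC is both cheaper and better on QALYs, ignoring the gain does not reverse the conclusion. All of this stands and limits the consequence. None of it makes a bounded loss a zero loss, or puts QALY uncertainty back into the cost interval.

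A reader might also infer three stronger claims that the documents do not support.

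- **That the saving is about four visits.** The protocol expects that "stepped care patients on step 1 of the intervention will have a median of three PC visits per patient by week 24", against a median of seven in the early integrated arm of the earlier trial. But 7 − 3 is a difference of medians, for step 1 patients only, up to week 24. The plan counts costs over the whole time in the trial. It includes inpatient, emergency, drug, other outpatient and patient time costs, and some patients will move to step 2. The visit difference is not the quantity that the rule compares, and the true saving could be larger or smaller.
- **That a wrong conclusion would occur with some stated probability.** Any such figure needs an invented QALY margin and SD. A probability of passing the gate also includes cases where favouring stepped PC is correct: with a $2,400 saving, a loss of 0.024 QALY is worth only $1,200.
- **That the plan will declare stepped PC the better value.** It says only that costs will be compared. A cost-only result under a cost-effectiveness endpoint invites that reading, but the protocol does not state it.

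**Conclusion.** The point holds as a structural fault in an exploratory analysis. The rule in Section 7.5 treats a one-sided bound on QALY loss as a zero difference, so it can point to stepped PC when its net benefit is negative, or discard a QALY gain. The missing QALY margin leaves the trigger undefined; that defect rests on the documents alone and needs no assumption.

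The size is best given as the break-even relation, total saving / $50,000. The dollar amounts put into it are illustrative assumptions. The threshold is the protocol's own. No frequency can be attached, and the primary and secondary conclusions do not depend on this rule. The change is still worth making, because the rule applies when the trial succeeds and no other text governs the economic analysis.

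**What to change.** Delete the switch from Protocol Section 7.5. Because the SAP leaves this analysis out and reports enrolment as complete, carry the replacement into whichever document will specify the economic analysis, before costs and QALYs are compared by arm.

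The replacement should say that, whatever the non-inferiority results:

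- cost and QALY differences are estimated jointly from patient-level pairs, for example by a paired bootstrap within the multiple imputation already planned;
- both differences are reported with intervals;
- the incremental net monetary benefit at $50,000 per QALY is reported with its interval;
- the cost difference is one component of the result, not the whole of it.

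With the switch gone, no QALY margin is needed for it. If the sponsor keeps any QALY non-inferiority gate, its margin must be stated and justified in advance.

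The cost is a change of wording and a little programming on data already planned (EQ-5D, cost records, imputation). The real downside is that the economic conclusion may be less certain than a cost-only comparison, because QALY uncertainty is then carried through.

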7.5.1. Stratification Factors and Intervention Allocation Plan

Patients will be randomized in 1:1 fashion and stratified by site (MGH vs. Duke vs. Penn) and underlying diagnosis (NSCLC vs. small cell lung cancer and mesothelioma). As patients with NSCLC have a significantly better prognosis than those with small cell lung cancer or mesothelioma, we will stratify by the underlying diagnosis to ensure adequate and balanced representation between the two study groups.

7.5.2. Stratification Factors and Their Impact on Design

Stratification factors do not impact the design of the study but will be considered during data analysis to compare baseline statistics and outcomes based on initial eligibility criteria to participate in the study. Post-hoc comparisons between patients with NSCLC and those with small cell lung cancer and mesothelioma will determine if different outcomes existed between these two groups.

7.5.3. Early Stopping Rules

Not applicable. Participants will be included in the study as long as they continue seeking care at the study sites. Death or discontinuation of clinic visits are the only reasons for participants to not be included in the full intervention.

7.5.4. Definition of and Allowance in Design for Unevaluable/Ineligible Participants

No unevaluable and/or ineligible participants will be included in this study.

7.5.5. Handling of Missing Data

The analyses will initially focus on patients who completed the 24-week assessment to compare stepped PC with early integrated PC without imposing assumptions about missing data. We will also use the intention-to-treat principle with all randomized subjects, conducting sensitivity analyses to explore how various assumptions about missing data and differences between completers and non-completers affect the estimated outcomes. If data appear to be missing at random, we will employ multiple imputation methods. However, if we find that participants do not complete assessments due to progressive illness, suggesting missing data are not random, we will employ pattern mixture modeling or terminal decline joint modeling approach to address missing data.

9.0. Appendices

9.1. Suggested Template for Emailing Clinicians: Permission to Approach Patient

Dear [MD/NP],

We are screening patients for the randomized study of stepped palliative care versus early integrated palliative care in patients with advanced lung cancer. As a reminder, ALL study patients will receive longitudinal, concurrent care from a palliative care clinician but the timing in which the visits are scheduled will vary by study group.

We plan to approach/contact [patient] [MRN] at one of their upcoming appointments to offer enrollment in this study. /We plan to contact [patient] [MRN] via telephone to offer enrollment in this study.

Please respond to this email if you prefer to approach the patient for study participation yourself or if you prefer that we do not approach this patient (and please indicate the reason why).

Thank you for your support,
[Study Principal Investigator]

9.2. Suggested Voicemail Script for Contacting Patients to Offer Enrollment

Hello, my name is [study staff member] and I am contacting [patient] from [institution] on behalf of [oncologist] to offer participation in a research study. If you are interested in learning more about this opportunity, please contact our study staff at [staff phone number] at your convenience. Thank you for your time.

9.3. Suggested Template for Emailing Oncology Clinicians: Notification about Step 1 Patients Following Enrollment

Dear [MD/NP],

Thank you for allowing me to meet with [patient] to introduce the Stepped Palliative Care study. After reviewing the details of the study and the consent form, [patient] signed consent and completed baseline measures. [Patient] will begin the study on Step 1 and will see palliative care at a reduced frequency following the initial visit. They will see palliative care again only following hospitalization or progression. Please plan to manage this patient's prescriptions, since they will not see PC regularly.

Thank you for your continued support of our study,
[Study Staff Member]

9.4. Suggested Template for Emailing Oncology Clinicians: Notification about Step 1 Patients on the Day of their First Oncology Appointment since Enrollment

Good morning,

You have an appointment with a Stepped Palliative Care [protocol number] study patient today.

[Last name, first name] (MRN) is on Step 1 of the study and [will see/is seeing] palliative care at a reduced frequency following the initial visit. They will see palliative care again only following hospitalization or progression. As a reminder, we will follow [patient name] closely and if their quality of life decreases, the palliative care visit frequency will increase to monthly. Please plan to manage this patient's prescriptions, since they will not see palliative care regularly.

Thank you for your continued support of our study,
[Study Staff Member]

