5.3. Description of Intervention

5.3.1. Stepped PC Arm

Patients who have been randomized to the stepped PC arm will be scheduled for an initial visit with the PC clinician either in person or via secure video visit within four weeks of enrollment. During step 1, additional visits with the PC clinician will be scheduled at clinically relevant points in the patients’ illness. In our recent study, we observed that over 80% of clinic visits that the PC clinicians recorded as “significant interactions” occurred after patients’ cancer progressed or a recent hospitalization. Therefore, during step 1, patients will be scheduled to meet with the outpatient PC clinician either in person or via secure video visit within four weeks after a change in cancer treatment (including radiation), or within four weeks of discharge from an inpatient admission. ‘Change in treatment’ for this study is defined as:

- i. A change in cancer treatment due to either progression or toxicity
- ii. A discontinuation of cancer treatment

Furthermore, if a step 1 patient is hospitalized within the first four weeks of enrollment, or if an inpatient admission occurs at any time, step 1 patients will default to the

procedure for hospitalizations and a PC appointment will be scheduled within four weeks of discharge. While hospitalized, step 1 patients may have inpatient PC appointments at the discretion of their oncology team, and such appointments will otherwise have no impact on study procedures.

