A study staff member will score the FACT-L within 5 business days of receiving the surveys. Step 1 patients whose FACT-L scores are found to decrease by ≥ 10 -points from baseline at any time during the study will be transitioned to Step 2 for the remainder of their illness. As outpatient PC is an available service at participating institutions, we will not deny patient or oncologist requests for additional PC visits for patients assigned to step 1. However, these visits will only be scheduled upon request and they will not trigger regularly scheduled visits every four weeks. In our prior study, only one-third of patients randomized to standard oncology care received a PC consultation based on request from the oncologist or the patient, with a median of 2 visits by 24 weeks. As step 1 patients will have PC visits at clinically relevant points in their illness, we anticipate few requests for additional PC visits for patients on step 1 of the stepped care intervention. For patients who are still on step 1 at 18 months from enrollment, PC scheduling will be at the discretion of their PC and oncology teams. Patients on Step 2 surviving greater than 18 months will be permitted to decrease the frequency of PC visits as per the discretion of their PC and oncology teams. Once patients are on hospice study visits will end, and further PC care will be per standard practice.

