5.3.3. Palliative Care Intervention Delivery

While the study protocol details the frequency of contact with a PC clinician, a variety of uncontrollable factors may impact intervention delivery. Patient factors include a change in their cancer treatment schedule, cancellation of cancer treatment, or fatigue that prohibits participation in a visit. Clinician factors include clinic delays leading to missed patient appointments and insufficient staffing, especially due to meetings and vacations. To reduce patient and clinician burden, we will conduct PC visits either in-person or via an institution-approved secure video platform. If an in-person or video visit cannot be scheduled, PC visits may be conducted via telephone. We will document missed contacts as minor violations and institute a corrective action plan if more than 15% of all planned patient contact with PC does not take place per study protocol at a study site.

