### *Stepped PC*

Patients randomized to stepped PC were scheduled for an initial visit with a PC clinician within 4 weeks of enrolment. During step 1, further visits with a PC clinician were scheduled at clinically significant points in the patient's illness, including within 4 weeks of (1) a change in cancer treatment (due to either progression or toxicity) or (2) hospital discharge. After each visit, the PC clinician communicated with the oncology clinician(s) either by telephone, email or in person. If a patient missed a scheduled visit or was unable to be scheduled for a PC visit, the PC clinician attempted to contact them by telephone and rescheduled the visit as soon as possible. Patients assigned to stepped PC completed the FACT-L every 6 weeks during the first 18 months of study participation. Those whose scores decreased by  $\geq 10$  points from baseline were 'stepped up' to step 2 and followed the same protocol as those randomized to the early integrated PC arm.

All study participants in both groups surviving greater than 18 months from enrolment were permitted to decrease the frequency of PC visits as per their preference and the discretion of their PC and oncology clinicians.

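### The suggested emails to oncologists say step 1 patients return to palliative care only after hospitalization or progression, which contradicts the visit triggers in Protocol 5.3.1

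*Protocol*

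**What the plan says.** Protocol 5.3.1 (Stepped PC Arm) schedules step 1 visits, after the initial one, "within four weeks after a change in cancer treatment (including radiation), or within four weeks of discharge from an inpatient admission". It then defines a change in treatment by two limbs: "A change in cancer treatment due to either progression or toxicity" and, separately, "A discontinuation of cancer treatment". The second limb carries no condition about cause. Later in the same section, on visits outside this schedule, the protocol says "we will not deny patient or oncologist requests for additional PC visits for patients assigned to step 1".

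The suggested emails in Protocol 9.3 (sent after enrollment) and 9.4 (sent on the day of the first oncology appointment since enrollment) both tell the oncology clinician: "They will see palliative care again only following hospitalization or progression". Template 9.4 adds that visits become monthly if quality of life falls. Neither template mentions toxicity, discontinuation or requested visits.

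SAP section 5 (Stepped PC) summarizes step 1 visits as "scheduled at clinically significant points in the patient's illness, including within 4 weeks of" "a change in cancer treatment (due to either progression or toxicity) or (2) hospital discharge". It has no separate discontinuation limb and does not mention radiation.

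**The concern.** Protocol 5.5.2 states that both arms follow the same intervention guide and differ only in how often and when patients engage with palliative care. The step 1 trigger rule is therefore a large part of what defines the experimental arm, and a misstatement of it in operational text is more than a matter of style.

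The emails go to the clinicians who change or stop cancer treatment and who may ask for extra visits. The word *only* is an affirmative statement that other visits do not occur. A clinician who relies on it would not expect a visit after a toxicity-driven switch or a planned stop, and might think a request was outside the study rules. If visits were lost in this way, the stepped arm would receive less contact than the model in 5.3.1. The count of outpatient palliative care visits through week 24, a secondary superiority outcome, would then move in favor of stepped care for a reason unrelated to the model's efficiency.

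**Working it through.** No sample-size or error-rate figure bears on this point, so the check sets the texts side by side. In the toxicity row and the last discontinuation row, the event is taken to occur without progression or an admission.

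| Event in a step 1 patient | Protocol 5.3.1 | Emails 9.3 and 9.4 | SAP section 5 |
|---|---|---|---|
| Discharge after an admission | Trigger | Trigger | Trigger |
| Progression leading to a treatment change | Trigger | Trigger | Trigger |
| Progression with no change or stop in treatment | Not a trigger | Trigger | Not named |
| Treatment change for toxicity | Trigger | Excluded by *only* | Trigger |
| Discontinuation because of progression | Trigger | Covered through progression | Can be read as a treatment change |
| Discontinuation for another reason | Trigger | Excluded by *only* | Not named, but the list is open |
| Visit requested by patient or oncologist | Not denied | Excluded by *only* | Not named |

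**Emails against protocol.** They disagree in four rows. In three of them (toxicity, discontinuation for another reason, requested visits) the emails are narrower. In one (progression without a change in treatment) they are wider. So the emails are not simply a shortened form of the protocol list.

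**SAP against protocol.** No row shows the SAP denying something that the protocol allows. Its list opens with a non-exhaustive word, and it describes delivery in the past tense. The difference is an omission.

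**Size.** With 255 patients planned in the stepped arm and two templates each, up to 2 × 255 = 510 emails could carry the sentence. That counts emails, not visits. Turning it into visits would need the rate of toxicity-driven changes, the rate of discontinuations for reasons other than progression, the rate of requests, and the share of each that is missed. None of these is in the documents.

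Two figures in 5.3.1 come close but do not fill the gap:

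- In the sponsor's recent study, over 80% of the visits that clinicians recorded as significant interactions followed progression or a recent hospitalization. It is tempting to take the remainder, under 20%, as an upper bound on the visits affected. It is not one: it describes which visits were judged significant, not how step 1 triggers divide.
- The expected median of three step 1 visits by week 24, against seven under early integrated care (1 − 3/7 = 57%, stated as about 60%), was estimated from rates of progression and hospitalization. That basis resembles the email list more than the full list in 5.3.1. It suggests how the shorter wording may have arisen, but says nothing about visits missed.

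**The case against.** The strongest case on the other side is that the emails need not change delivery. They are headed as suggestions, and 5.3.1 is the operative text. Their practical message is that contact will be less frequent and that the oncologist should manage prescriptions; they do not ask oncologists to report triggers or book visits. Template 9.11 shows a research coordinator contacting the patient to arrange the palliative care appointment. Palliative care clinicians also try to update oncology about each step 1 visit, so the emails are not the oncologist's only information. This stands: a wrong email need not produce a missed visit. It does not remove the contradiction, and the documents do not say who detects a trigger, so an effect through the oncologist cannot be ruled out either.

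Timing is a second objection. The SAP (version 1.0, October 2023) describes the 510 patients as already enrolled, so most of these emails will have been sent. This also stands. It moves the remedy from prevention toward reporting.

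A reader might go further and infer that the protocol, emails and SAP give three mutually contradictory rules, so that adherence has no single standard. The documents do not support that. The SAP list is open-ended. The protocol's only numerical adherence rule, in 5.3.3, is to "institute a corrective action plan if more than 15% of all planned patient contact with PC does not take place per study protocol", which already points to the protocol text. No planned analysis is computed from a trigger list: the visit outcome counts outpatient visits documented in the health record, and the per-protocol analyses in SAP section 8 are conditional, post hoc and not tied to the SAP's summary of triggers.

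**Conclusion.** The contradiction between the emails (9.3 and 9.4) and Protocol 5.3.1 is established on the text, and it runs in both directions. It misinforms the clinicians who change or stop treatment about when the experimental arm is seen. Fewer expected or requested visits is a plausible consequence, but it rests on the assumption that oncologists' expectations affect whether visits happen, and its size cannot be computed from the documents.

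A reader might infer that the stepped arm was under-delivered, or that the non-inferiority test on the FACT-L is compromised. Neither follows. No missed visit is shown, and the primary analysis is by intention to treat, so the trigger wording does not enter the test directly. The SAP's missing discontinuation limb is a minor matter of alignment. This is an inexpensive correction that should be made, not a threat to the trial's validity. Which triggers are clinically appropriate is not judged here.

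**What to change.** 1. Reconcile templates 9.3 and 9.4 with Protocol 5.3.1, including its provision on requested visits, so that the emails carry the same step 1 triggers as the operative text. Drop *only*, which cannot stand beside the requested-visit provision.
2. As a minor alignment, have the step 1 summary in SAP section 5 refer to the reconciled protocol list instead of giving its own. If a per-protocol analysis under SAP section 8 is run, state that this list defines the required step 1 visits. The existing SAP addendum is a natural place for both.
3. Where emails have already been sent, state in the report which trigger list was applied in practice and that the emails differed from the protocol.

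The cost is two template edits, one SAP or addendum sentence and a short statement in the report. No change to the sample size, the endpoints or the primary analysis is needed.
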